7.2.4. Strategy for Intercurrent (Post-Randomisation) Events

Refer to Section [7.1.4](#) Strategy for Intercurrent (Post-Randomisation) Events

7.2.5. Statistical Analyses / Methods

Details of the planned displays are provided in [Appendix 12](#): List of Data Displays and will be based on GSK data standards and statistical principles.

Unless otherwise specified, endpoints / variables defined in Section [7.2.1](#) will be summarised using descriptive statistics, graphically presented (where appropriate) and listed.

Table 3 Exploratory PainCart Analyses

Estimand	Endpoint	Summary*	Analysis – Bayesian AAUC Mixed ANCOVA	Listing
Cold Pressor	Detection	Yes	Yes	Yes
Electrical pain – single stimulus	Detection	Yes	Yes	Yes
Electrical pain – repeat stimulus	Detection	Yes	Yes	Yes
	Tolerance	Yes	Yes	Yes
Conditioned pain modulation	Detection	Yes	Yes	Yes
	Tolerance	Yes	Yes	Yes
Heat Pain	Detection (Normal Skin)	Yes	No	Yes
Pressure Pain	Detection	Yes	No	Yes
	Tolerance	Yes	No	Yes

*The summary will include summary statistics for the summary measures, AAUC and post-test eVAS scores.

Note: ANCOVA analyses will be performed in the Bayesian framework only.

7.2.5.1. Statistical Methodology Specification

Endpoint / Variables

 The endpoints will be analysed as detailed in Section 7.1.5.1.
Model Specification

 Refer to Section 7.1.5.1.2 Model Specification for more information
Model Checking & Diagnostics

 Refer to Section 7.1.5.1.2 Model Checking and Diagnostics for more information
Model Results Presentation

 Refer to Section 7.1.5.1.2 Model Results Presentation for more information

7.3. Serum Target Engagement Analyses

The Target Engagement analyses described below will be carried out for Free and Total CCL17 in Serum. The target engagement analyses will be based on the Safety population, unless otherwise specified.

7.3.1. Endpoint / Variables

7.3.1.1. Target Engagement Concentration Measures

Refer to [Appendix 5](#) Section [12.5.4](#) Reporting Standards for Target Engagement.

7.3.1.2. Derived Target Engagement Parameters

All calculations will be based on actual sampling times.

Target engagement parameters listed below will be determined from the observed free CCL17 levels in serum. Additional parameters may be included as required.

Parameter	Parameter description
Cmin	
 Minimum observed concentration Determined directly from the concentration-time data
tmin	
 Time to reach Cmin Determined directly from the concentration-time data
BL	
 Baseline (as defined in Section 5.2)
Percentage reduction	
 Percentage of free CCL17 reduced by the presence of GSK3858279 Calculated by time point as: $(BL - concentration) * 100 / BL$
Maximum Percentage reduction	
 Maximum Percentage of free CCL17 reduced by the presence of GSK3858279 Calculated as: $(BL - Cmin) * 100 / BL$

NOTES:

Additional parameters may be included as required.

Target engagement parameters listed below will be determined from the observed total CCL17 levels in serum. Additional parameters may be included as required.

Parameter	Parameter description
Cmax	
 • Maximum observed concentration • Determined directly from the concentration-time data
tmax	
 • Time to reach Cmax • Determined directly from the concentration-time data
BL	
 • Baseline (as defined in Section 5.2)
Fold increase	
 • Ratio of total CCL17 concentration to baseline • Calculated by time point as: Concentration/BL • Determined directly from the concentration-time data
Maximum Fold increase	
 • Ratio of maximum concentration of total CCL17 to baseline • Calculated as: Cmax/BL • Determined directly from the concentration-time data

NOTES:

Additional parameters may be included as required.

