4.4. Justification for Dose and Washout Period

The dose level of 3mg/kg, the 2-week testing duration of each study period, the wash out period of at least 4 weeks, the IV route of administration and the post dose assessment times of Day 1, Day 2, Day 8 and Day 15 are selected for the PainCart study based on:

The dose by IV route is equivalent to the dose of 240mg SC proposed to be administered in an on-going repeat dose study in osteoarthritis patients (207804) and was administered in a healthy participant cohort in that study (3 mg/kg IV). Serum levels of total (complexed, free and partially complexed) GSK3858279 are below the lower limit of quantification (LLQ; 100 ng/mL) after 8 weeks following IV infusion at 3 mg/kg; based on data from a fully validated non-neutralising anti-idiotype capture (NNAIC) assay [GlaxoSmithKline Document Number [2020N429762_00](#)].

- Unbound CCL17 levels in serum have returned to approximately 30% of baseline at 4 weeks post dose.
 - A simulation plan was designed in order to investigate whether the statistical modelling for the PainCart assessments could control the potential properties of carry over effect. The plan details simulating carry over by varying different levels of drug accumulation in to the subsequent period, and the number of days it took for the drug to be eliminated. The results from the simulation showed even in the most extreme scenario (40% accumulation, 2 weeks reduction) the model was capable of extracting the treatment differences while controlling any potential carry over effects.
 - Given the statistical model chosen for analysis, and no increase in risk of safety, the washout period of at least 4 weeks is selected and still considered sufficient (data on file).
- Target engagement (percentage reduction from baseline of free CCL17) is above 90% within 24 hours of dosing IV and continues to 1-week post IV dose of 3 mg/kg. TE falls to 75% after 2 weeks post dose IV.
- t_{max} is at end of IV dose administration allowing PainCart testing to be scheduled at consistent fixed timepoints relative to dosing.

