5.2. Baseline Definitions

For all endpoints (except as noted in baseline definitions) the baseline value will be the latest pre-dose assessment with a non-missing value, including those from unscheduled visits. This study has three study periods, with each period having its own baseline which is the latest non-missing value prior to dosing in that period.

For the PainCart test, two assessments are performed at each visit except for visit Day 1 where two are performed prior to dose and two are performed after dose. The baseline value is defined as the mean of the two pre-dose assessments on Day 1 for each study period. If only one pre-dose assessment record is present on Day 1, then this value will be set as the baseline value.

For the PainCart analyses, baseline will compose of two variables:

- Subject level baseline = the mean of the three period baseline values for each subject.
- Period level baseline = Subject level baseline – Period specific baseline value.

Parameter	Study Assessments Considered as Baseline			Baseline Used in Data Display
	Screening	Day -1	Day 1 (Pre-Dose)	
Efficacy				
PainCart Assessments			X	Mean of Day 1 (Pre-Dose) Assessments
Safety				
Vital Signs			X	Day 1 (Pre-Dose)
Haematology			X	Day 1 (Pre-Dose)
Chemistry			X	Day 1 (Pre-Dose)
ECG			X	Day 1(Pre-Dose) [Mean of triplicate measurements]
Urinalysis			X	Day 1 (Pre-Dose)

Unless otherwise stated, if baseline data is missing no derivation will be performed and baseline will be set to missing.

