7.3.2. Statistical Analyses / Methods

Details of the planned displays are provided in [Appendix 12: List of Data Displays](#) and will be based on GSK Data Standards and statistical principles.

Unless otherwise specified, endpoints / variables defined in Section 7.3.1 will be summarised using descriptive statistics by treatment and study period, graphically presented (where appropriate) and listed.

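### Percentage reduction of free CCL17 uses each period's own pre-dose value, so it is likely understated in the two periods that directly follow GSK3858279

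*SAP*

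**What the plan says.** SAP section 7.3.1.2 describes the by-time-point parameter as "Percentage of free CCL17 reduced by the presence of GSK3858279". It is the baseline (BL) minus the concentration, times 100, divided by BL. BL is given as "Baseline (as defined in Section 5.2". Section 5.2 makes an exception only for PainCart, so free CCL17 falls under the general rule of "each period having its own baseline which is the latest non-missing value prior to dosing in that period". SAP section 12.5.4 adds rules for missing or zero CCL17 baselines but nothing for a baseline that still carries drug effect.

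Section 7.3.2 states that these parameters "will be summarised using descriptive statistics by treatment and study period". SAP section 5.1 lists two sequences, A/P/P and P/A/A.

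On residual effect, protocol section 4.4 reports: "Unbound CCL17 levels in serum have returned to approximately 30% of baseline at 4 weeks post dose". It adds that total drug levels "are below the lower limit of quantification (LLQ; 100 ng/mL) after 8 weeks following IV infusion at 3 mg/kg". The protocol synopsis sets the interval between doses at a minimum of four weeks; the design features in SAP section 2.3 put it at approximately four weeks.

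**The concern.** A measure of how far the drug lowers free CCL17 needs an untreated reference. In two of the six sequence-by-period cells the reference is taken after an earlier active dose and may still be low: P/A/A Period 3 (active after active) and A/P/P Period 2 (placebo after active). There the formula measures only the change from residual suppression, which is not what section 7.3.1.2 says it measures. Nor is the result comparable with the engagement figures that protocol section 4.4 uses to justify the dose.

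With two sequences, the GSK3858279 Period 3 row consists entirely of P/A/A participants and the Placebo Period 2 row entirely of A/P/P participants. In Tables 2.23 and 2.24 and Listings 36 and 37, a second dose could look weaker than a first at time points such as Day 15, and placebo could show negative reductions. The carry-over simulation in protocol section 4.4 concerns the PainCart model; the target engagement summaries use no model.

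**Working it through.** **Inputs.** Set the untreated level of free CCL17 to 100, let *B* be the pre-dose value of the period and *c* a later value.

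- From protocol section 4.4: engagement is above 90% up to one week (*c* = 10 as the bound) and 75% at two weeks (*c* = 25). Free CCL17 is about 30% of baseline at four weeks (*B* = 30).
- Alternative reading of that last figure, as having come back to within 30% of baseline: *B* = 70.
- Assumed, to show the range: *B* = 50, *B* = 85 and *c* = 1.
- Assumed: a second dose brings free CCL17 to the same levels as a first.

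**Plan's own figures.** With *B* = 100, 100 × (100 − 10)/100 = 90% and 100 × (100 − 25)/100 = 75%. This is an identity, not an independent reproduction, because the earlier study's data are not in the documents.

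**Direction.** The SAP value minus the value against the untreated level is 100 × *c* × (1/100 − 1/*B*). This is negative for every *c* above zero whenever *B* is below 100.

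**Active after active (P/A/A Period 3).** SAP value = 100 × (*B* − *c*)/*B*. For example, with *B* = 30 and *c* = 25, 100 × 5/30 = 16.7%.

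| Pre-dose *B* | True 75% (*c* = 25) | True 90% (*c* = 10) | True 99% (*c* = 1) |
|---|---|---|---|
| 30 | 16.7% | 66.7% | 96.7% |
| 50 | 50.0% | 80.0% | 98.0% |
| 70 | 64.3% | 85.7% | 98.6% |
| 85 | 70.6% | 88.2% | 98.8% |

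**Placebo after active (A/P/P Period 2).** As free CCL17 recovers, *c* exceeds *B* and the SAP value is negative. The documents do not give the recovery, so no size is claimed.

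**Interval between doses.** The stated total of about six months is 26 weeks. Taking off 4 weeks of screening and 8 of follow-up leaves 14 weeks over two intervals, about 7 weeks each. At four-week intervals the total would be 4 + 4 + 4 + 8 = 20 weeks, or 4.6 months. Actual intervals may therefore exceed the minimum, which would raise *B* and shrink the error. The documents give no free CCL17 level at 7 weeks.

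**Other cells.** Period 1 of both sequences is untreated at baseline, and P/A/A Period 2 follows placebo. A/P/P Period 3 starts at least 8 weeks after active drug; its residual free CCL17 is not given and nothing is claimed for it.

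**The case against.** The strongest reply concerns size and consequence. Protocol section 4.4 has free CCL17 at no more than 10% at one week and 25% at two weeks. A literal 30% at four weeks then means a rise of at least 15 points in the second week but only 5 over the next two. The within-30% reading fits that recovery at least as well, and under it the errors are about 11 and 4 points. Intervals nearer 7 weeks would shrink them further. The cause can also be traced: Tables 2.22 and 2.23 give concentrations and baselines by treatment and period, and Figures 2.07 to 2.09 plot the concentrations by sequence with the periods overlaid. A period-specific baseline is a legitimate measure of change within a period. A Period 1 baseline has its own weakness, since one early value, possibly an imputed median, serves three periods.

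Most of this stands as a limit on size and importance. It does not remove the point. The direction holds under either reading, as long as the pre-dose value is below the untreated level. The concentration displays help a careful reader but leave the percentages uncorrected. Change within a period is not the quantity section 7.3.1.2 describes.

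**Conclusion.** The concern holds. In P/A/A Period 3 and A/P/P Period 2 the SAP's percentage reduction is measured from a baseline that is likely still suppressed. A true 75% would read between 17% and 71%, and a true 90% between 67% and 88%, for pre-dose values from 30% to 85% of untreated. The 30% row is the worst case considered: a four-week interval with the protocol figure taken literally. All rows assume that the second dose acts like the first.

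Maximum percentage reduction changes little if suppression is near complete, and no distortion of it is claimed. Fold increase in total CCL17 follows the same baseline rule, but the documents give no residual total level, so no size is claimed there either.

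The consequence is confined to exploratory, descriptive displays. The PainCart models, the six PK/PD figures and the futility decision, which rests on the cold pressor and electrical endpoints, do not use this parameter. The study has already stopped, but the tables and listings are still due in the final package, so the correction is worth making.

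**What to change.** In SAP section 7.3.1.2, derive percentage reduction, fold increase and their maxima against the Period 1 Day 1 pre-dose value in all periods. Show the period-specific version alongside in Tables 2.23 and 2.24 and Listings 36 to 38. Including the maxima and fold increase keeps one baseline rule for all the ratios. Add two footnotes:

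1. Placebo Period 2 (A/P/P) values against the Period 1 baseline reflect residual engagement from the earlier active dose, not a placebo effect. The pre-dose value in P/A/A Period 3 carries the same residual.
2. Period-specific values in these two cells use a baseline that may be suppressed.

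Record the change in SAP Table 1 as made after the interim.

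The cost is one sentence, two footnotes and a second derivation from a sample already in the schedule; section 7.3.1.2 already allows that "Additional parameters may be included as required". There are two drawbacks. Natural drift, and any median imputed for a missing baseline under section 12.5.4, would carry through all three periods. Residual engagement would also appear in the Placebo Period 2 rows: a pre-dose value of 30, 50, 70 or 85 against 100 reads as a 70%, 50%, 30% or 15% reduction, which is why the first footnote is needed.

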7.3.2. Statistical Analyses / Methods

Details of the planned displays are provided in [Appendix 12: List of Data Displays](#) and will be based on GSK Data Standards and statistical principles.

Unless otherwise specified, endpoints / variables defined in Section 7.3.1 will be summarised using descriptive statistics by treatment and study period, graphically presented (where appropriate) and listed.

7.4. Immunogenicity

7.4.1. Summary Measure

The number and percentage of confirmed positive samples in each treatment group and period will be presented at each time assessed.

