2.3. Study Design

This study will be a randomized, double-blind, placebo-controlled, three-period two-treatment incomplete-block crossover study in healthy participants to investigate the effects of IV GSK3858279 on evoked pain tests in the PainCart. The study will be performed in a single centre.

In each period participants will receive either GSK3858279 or placebo in a 1:1 ratio. During the trial participants will receive both treatments, participants will receive either two doses of GSK3858279 and one dose of placebo, or two doses of placebo and one dose of GSK3858279 with equal likelihood, the order of treatment assignments will be randomised.

The total duration of the study (from signing informed consent until final follow-up visit) for each participant will be approximately 6 months. Study participation may be prolonged in the event the study is on-hold. Screening period will be a maximum of 28 days prior to study procedures, each study period will be approximately 2 weeks with at least a 4-week wash-out period between dosing (i.e. Day 1) in each of the study periods, final follow-up visit will be at approximately 8 weeks after last dose.

Participants will arrive at the research unit either one or two days before dosing, for the non-UVB-MITT and UVB-MITT group respectively. After arrival, subjects will be tested for SARS-CoV-2. Urine will be screened for the presence of drugs and an alcohol breath test will be performed. For participants with a positive urine drug screen or alcohol breath test, the treatment occasion may be rescheduled at the discretion of the principal investigator and GSK medical monitor. UVB irradiation will be applied approximately 24 hours before dosing in the UVB-MITT population only. ECG and vital signs will also be performed.

Participants will be assigned to receive treatment and pain assessments during either morning or afternoon sessions. They will continue to receive treatment and pain assessments at approximately the same time of day throughout all three study periods.

Meals will be served at the site scheduled times. Safety, PK, PD and PainCart assessments will be performed as outlined in the SoA. Baseline measurements for PainCart (2 baseline measurements) are conducted at each study period prior to dosing.

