4. ANALYSIS POPULATIONS

Population	Definition / Criteria	Analyses Evaluated
Screened	
 • All participants who were screened for eligibility 	
 • Study Population • Safety
Enrolled	
 • All participants who passed screening and entered the study. • Note screening failures (who never passed screening even if rescreened) and participants screened but never enrolled into the study (Reserve, Not Used) are excluded from the Enrolled population as they did not enter the study. 	
 • Study Population
Randomized	
 • All participants who were randomly assigned to treatment in the study. • This population will be based on the treatment sequence the participant was randomized to. 	
 • Study Population
Safety	
 • All randomized participants who received at least one dose of study treatment. • This population will be based on the treatment sequence the subject actually received. • Note: Participants who were not randomized but received at least one dose of study treatment should be included. 	
 • Safety • PK/PD
Pharmacokinetic (PK)	
 • All participants in the Safety population who had at least 1 non-missing serum PK assessment. • Note: Non-quantifiable [NQ] values will be considered as non-missing values 	
 • PK
Intent-To-Treat (ITT)	
 • All randomized participants who received at least one dose of study treatment. • This population will be based on the treatment sequence the subject was randomized to. • Any participants who receives a treatment randomization number will be considered to have been randomized. 	
 • PainCart • Study Population
Modified Intent-to-Treat (MITT)	
 • All randomized participants who received at least one dose of study treatment and completed at least one PainCart assessment in at least two study periods. • This population will be based on the treatment sequence the subject was randomized to. • Any participants who receives a treatment randomization number will be considered to have been randomized. 	
 • PainCart

Population	Definition / Criteria	Analyses Evaluated

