5. CONSIDERATIONS FOR DATA ANALYSES AND DATA HANDLING CONVENTIONS

5.1. Study Treatment & Sub-group Display Descriptors

Treatment Group Descriptions			
RandAll NG		Data Displays for Reporting	
Code	Description	Description	Order in TLF
A	3 mg/kg IV GSK3858279	GSK3858279	2
P	Placebo	Placebo	1

Treatment comparisons will be displayed as follows using the descriptors as specified:

1. GSK3858279 vs Placebo

For treatment sequence displays:

Treatment Group Descriptions			
RandAll NG		Data Displays for Reporting	
Code	Description	Description	Order in TLF
A/P/P	3 mg/kg IV GSK3858279 – Placebo – Placebo	GSK3858279-Placebo-Placebo	2
P/A/A	Placebo – 3 mg/kg IV GSK3858279 – 3 mg/kg IV GSK3858279	Placebo- GSK3858279- GSK3858279	1
		Total	3

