12.6. Appendix 6: Derived and Transformed Data

12.6.1. General

Multiple Measurements at One Analysis Time Point	

 Mean of the measurements will be calculated and used in any derivation of summary statistics but if listed, all data will be presented. Participants having both High and Low values for Normal Ranges at any post-baseline visit for safety parameters will be counted in both the High and Low categories of “Any visit post-baseline” row of related summary tables. This will also be applicable to relevant Potential Clinical Importance summary tables. 	
Study Period	

 The start date of Period [1/2/3] is the dosing Day 1 date for that period. The end date of Period [1/2] is the Day -1 date for the subsequent period. The end date for Period 3 and Period[1/2] if no subsequent period follows, will be the final follow up visit date, or if applicable, study withdrawal date, whichever date is earlier. 	
Study Day / Period Day	

 Study day is derived with respect to the very first dose date (Period 1): 
 Ref Date = Missing → Study Day = Missing Ref Date < Dose Date → Study Day = Ref Date – Dose Date Ref Date ≥ Dose Date → Study Day = Ref Date – (Dose Date) + 1 Period day is derived with respect to the dose date during that period: 
 Ref Date = Missing → Period Day = Missing Ref Date < Period Start Date → Period Day = Ref Date – Period Dose Start Date Ref Date ≥ Period Start Date → Period Day = Ref Date – (Period Dose Start Date) + 1 	

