2.24.	Safety	PD_T7	Summary of Derived Free and Total CCL17 in Serum Target Engagement Parameters - Percent Reduction and Fold Increase (non-transformed and log-transformed)	By treatment & study period. Include a column Planned Time Point.	IA 1 [1], AAC [2]

Pharmacodynamic: Tables					
No.	Population	IDSL / Example Shell	Title	Programming Notes	Deliverable [Priority]
Immunogenicity					
2.25.	Safety	IMM1	Summary of Immunogenicity	Present by Period. Drop Planned Time Column. Include a Total Column. Footnote: "Note: Percentage is calculated as $(x/n) * 100$ where x = the number of subjects with a positive sample and n = the number of subjects for whom a sample was collected."	AAC [1]

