12.11.7. Safety Tables

Safety: Tables – All Safety Tables will be presented by Period unless stated otherwise.					
No.	Population	IDS / Example Shell	Title	Programming Notes	Deliverable [Priority]
Adverse Events (AEs)					
3.01.	Safety	AE1xo	Summary of All Adverse Events by System Organ Class and Preferred Term by Period	ICH E3 Present by Period Programming note: For interim analysis present AEs SOCs and PTs which have more than 2 subjects overall per period. i.e. at least two unique subjects in the Total column per period. Include footnote: Note: For interim, only AEs occurring in two or more subjects by period are reported.	IA 1 [1], IA 2 [2], SAC [3]
3.02.	UVB-Safety	AE1xo	Summary of All Adverse Events by System Organ Class and Preferred Term by Period – UVB Participants Only	ICH E3 Present by Period	SAC [1]
3.03.	Safety	AE1xo	Summary of All Adverse Events by System Organ Class and Preferred Term - Overall	ICH E3 Present Placebo, GSK3858279, Total Columns	SAC [1]
3.04.	Safety	AE5A	Summary of All Adverse Events by System Organ Class and Preferred Term and Maximum Intensity by Period	ICH E3	SAC [1]
3.05.	Safety	AE1xo	Summary All Drug-Related Adverse Events by System Organ Class and Preferred Term by Period	ICH E3	SAC [1]
3.06.	Safety	AE5A	Summary of All Drug-Related Adverse Events by System Organ Class and Preferred Term and Maximum Intensity by Period	ICH E3	SAC [1]
3.07.	Safety	AE3	Summary of Non-Serious Drug-Related Adverse Events by Overall Frequency by Period	PLS Requirement	SAC [1]

Safety: Tables – All Safety Tables will be presented by Period unless stated otherwise.					
No.	Population	IDSL / Example Shell	Title	Programming Notes	Deliverable [Priority]
3.08.	Safety	AE15	Summary of Common (>=5%) Non-serious Adverse Events by System Organ Class and Preferred Term (Number of Participant and Occurrences) by Period	FDAAA, EudraCT	SAC [1]
Serious and Other Significant Adverse Events					
3.09.	Safety	AE16	Summary of Serious Adverse Events by System Organ Class and Preferred Term (Number of Participants and Occurrences) by Period	FDAAA, EudraCT Produce if more than 5 SAEs are reported.	SAC [1]
3.10.	Safety	AE3	Summary of Serious Drug-Related Adverse Events by Overall Frequency by Period	PLS Requirement	SAC [1]

Safety: Tables – All Safety Tables will be presented by Period unless stated otherwise.					
No.	Population	IDSL / Example Shell	Title	Programming Notes	Deliverable [Priority]
Laboratory: Chemistry					

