3.11.	Safety	LB1	Summary of Chemistry Changes from Baseline by Period	ICH E3 Present by Period	AAC [1]
3.12.	Safety	LB17	Summary of Worst-Case Chemistry Results by PCI Criteria Post-Baseline Relative to Baseline by Period	ICH E3 Present by period	AAC [1]
Laboratory: Haematology					
3.13.	Safety	LB1	Summary of Haematology Changes from Baseline by Period	ICH E3 Present by Period	AAC [1]
3.14.	Safety	LB17	Summary of Worst Case Haematology by PCI Criteria Post-Baseline Relative to Baseline by Period	ICH E3 Present by Period	AAC [1]
Laboratory: Urinalysis					
3.15.	Safety	LB1	Summary of Urine Concentration Changes from Baseline by Period	ICH E3 Present by Period	AAC [1]
3.16.	Safety	UR1	Summary of Worst-Case Urinalysis Results (Discrete or Character Values) Post-Baseline Relative to Baseline by Period	ICH E3 Present by Period	AAC [1]
ECG					
3.17.	Safety	EG1	Summary of ECG Findings by Period	IDSL	AAC [1]
3.18.	Safety	EG10	Summary of Maximum QTc Values Post-Baseline Relative to Baseline by Category by Period	IDSL	AAC [1]

CONFIDENTIAL

209973

Safety: Tables – All Safety Tables will be presented by Period unless stated otherwise.					
No.	Population	IDSL / Example Shell	Title	Programming Notes	Deliverable [Priority]
3.19.	Safety	EG2	Summary of Change from Baseline in ECG Values by Day by Period	IDSL	AAC [1]
3.20.	[Safety]	EG11	Summary of Maximum Increase in QTc Values Post-Baseline Relative to Baseline by Category by Period	IDSL	AAC [1]
Vital Signs					
3.21.	Safety	VS1	Summary of Change from Baseline in Vital Signs by Period	ICH E3	AAC [1]
3.22.	Safety	VS7	Summary of Worst-Case Vital Signs Results by PCI Criteria Post-Baseline Relative to Baseline by Period	IDSL	AAC [1]
Laboratory: Hepatobiliary (Liver)					
3.23.	Safety	LIVER1	Summary of Liver Monitoring/Stopping Event Reporting by Period	IDSL Programming Note: Subjects should be recorded under the treatment they are receiving at the time the liver monitoring/stopping event is reported, or if the liver monitoring/stopping event was reported during a washout period, under the last study treatment received. Only produce if there is a liver event	AAC [1]

CONFIDENTIAL

209973

Safety: Tables – All Safety Tables will be presented by Period unless stated otherwise.					
No.	Population	IDSL / Example Shell	Title	Programming Notes	Deliverable [Priority]
COVID-19					

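### The antibody summary ignores status before the first GSK3858279 dose, and if grouped by current treatment its Period 2 and 3 placebo cells hold only previously exposed participants

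*SAP*

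**What the plan says.** SAP 7.4.1 gives the immunogenicity summary: "The number and percentage of confirmed positive samples in each treatment group and period will be presented at each time assessed". The analysis uses the Safety population (SAP 7.4.2), of which SAP 4 says: "This population will be based on the treatment sequence the subject actually received". SAP 5.1 lists two sequences. One is "GSK3858279 – Placebo – Placebo" (A/P/P); the other is its mirror image, P/A/A. The section uses the same heading for the table of treatments and the table of sequences.

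Table 2.25 (SAP 12.11.5) is the only immunogenicity table. Its programming note reads: "Present by Period. Drop Planned Time Column. Include a Total Column". Its footnote defines the percentage as participants with a positive sample over participants sampled. The objective in SAP 2.2 is to assess antibody formation after IV dosing. The only treatment-emergent flag in the SAP is for adverse events (SAP 12.4.2). Neither SAP 7.4, Table 2.25 nor protocol 8.8 defines one for antibodies.

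**The concern.** An antibody to GSK3858279 can outlast the period in which the drug was given, or first appear after it. A count by treatment and period is therefore easy to read only if the label of the cell tells the reader who has been exposed. In A/P/P the active dose comes first and both later periods are placebo. A count under the current treatment would place later-appearing antibodies in the placebo column.

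Whichever way the cells are labelled, a count of all positives mixes antibodies present before any GSK3858279 with those that arose afterwards. The first-in-human study found a low but non-zero incidence of pre-existing antibodies (protocol 2.3.1), so the distinction is not empty. At stake is whether the planned summary answers the stated objective, which concerns formation after dosing.

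**Working it through.** **Inputs.** Sequences A/P/P and P/A/A (SAP 5.1); 1:1 allocation in each period (protocol 6.3.1); at most 30 randomised and about 24 completing (protocol 9.2); antibody samples at Day 1 pre-dose and Day 15 of each period (note in the schedule, SAP 12.2.1.2). On periods, SAP 12.6.1 says "The start date of Period [1/2/3] is the dosing Day 1 date for that period". On spacing, SAP 2.3 gives "at least a 4-week wash-out period between dosing (i.e. Day 1) in each of the study periods".

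**Step 1, the plan's own ratio.** With 30 participants and equal allocation, each sequence has 30/2 = 15. Every period then has 15 on GSK3858279 and 15 on placebo, which reproduces 1:1.

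**Step 2, earlier GSK3858279 exposure by current-treatment cell.**

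| Period | Placebo cell | GSK3858279 cell |
|---|---|---|
| 1 | 0/15 | 0/15 |
| 2 | 15/15 | 0/15 |
| 3 | 15/15 | 15/15 |

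With 24 completers the denominators become 12 and the shares do not change. At the Period 2 pre-dose sample the labels run opposite to exposure: the placebo cell is fully exposed and the GSK3858279 cell is drug-naive.

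**Step 3, samples per participant.** A pre-dose sample is taken on the dosing date, so by date it belongs to the new period.

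| Sequence | Period 1 | Period 2 | Period 3 | Post-exposure |
|---|---|---|---|---|
| A/P/P | naive, post | post, post | post, post | 1 + 2 + 2 = 5 |
| P/A/A | naive, naive | naive, post | post, post | 0 + 1 + 2 = 3 |

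If the label follows the period, 2 + 2 = 4 of the 5 post-exposure A/P/P samples are placebo-labelled. Table 3.23 offers another rule, for liver events: "Subjects should be recorded under the treatment they are receiving at the time the liver monitoring/stopping event is reported", with events in washout placed under the last treatment received. By analogy the A/P/P Period 2 pre-dose sample, taken before any placebo, moves to GSK3858279, leaving 3 of 5. The Period 3 pre-dose sample stays with placebo. Early Withdrawal samples are not counted.

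**Step 4, timing.** At the minimum spacing, the four A/P/P samples after Period 1 fall at 4, 4 + 2 = 6, 8 and 8 + 2 = 10 weeks after the active dose. The follow-up schedule (SAP 12.2.1.1) lists no antibody sample.

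**Step 5, sensitivity.**
- The protocol does not list the sequences. If all six three-period sequences containing both treatments were used, the Period 2 placebo cell would be 10/15 exposed and the Period 3 placebo cell still 15/15.
- In the schedule as supplied, the second mark sits under Day 8 while the note says Day 15; this may come from the file conversion. If Day 8 replaced Day 15, the counts stay at 4 (or 3) of 5. If both days were sampled, they become 6 (or 5) of 8.

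**Step 6, can the general baseline rule help?** SAP 5.2 gives each period its own baseline, the latest value before that period's dose. Take an A/P/P antibody that arises between Period 1 Day 15 and Period 2 pre-dose. It becomes the Period 2 baseline and would be classed as pre-existing. The rule does not separate induced from pre-existing antibodies.

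**Step 7, text against table.** Section 7.4.1 counts samples at each time; Table 2.25 counts participants and drops the planned time column. At a single time the two units coincide. They differ only if times are pooled.

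**The case against.** The strongest reply is that *treatment group* may mean sequence. SAP 5.1 allows it, the Safety population is sequence-based, and the mean and median concentration figures are drawn by sequence (SAP 12.11.6 and 12.11.9). On that reading nothing is mislabelled. Even on the other reading, two sequences make treatment-by-period cells identical in membership to sequence-by-period cells, so a reader who knows the design can recover exposure. This stands, and it makes the labelling half of the point conditional. The current-treatment reading is still reasonable: SAP 7.3.2 summarises target engagement by treatment and period, and Table 3.24 is a by-period table with placebo and GSK3858279 columns. Table 3.03 ("Present Placebo, GSK3858279, Total Columns") adds no support, because it is an overall table.

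Three stronger inferences are tempting, and the documents do not support them.
- A reader might conclude that pre-dose and Day 15 samples are certainly pooled. That depends on the IMM1 shell, which was not supplied. If it keeps visit rows, dropping the time column is harmless.
- A reader might conclude that late antibodies in A/P/P can be seen only under placebo. The schedule also has an Early Withdrawal antibody sample. For someone leaving before Period 2, SAP 12.6.1 extends Period 1, so that sample could fall under GSK3858279.
- A reader might conclude that nothing is shown after the first active dose. If 7.4.1 is followed as written, Day 15 of Period 1 (A/P/P) and of Period 2 (P/A/A) stand beside their pre-dose counts. Those are separate totals, however, and do not show which participants turned positive.

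**Conclusion.** The point holds as a minor weakness of the summary measure. On either reading, SAP 7.4.1 and Table 2.25 count positives without reference to status before the first GSK3858279 dose, so induced incidence is not reported as such. On the current-treatment reading, two of the three placebo cells are wholly previously exposed, and 3 or 4 of 5 scheduled post-exposure A/P/P samples are labelled placebo. An antibody first detected at a scheduled sample after Period 1 in that sequence would then appear mainly as a placebo positive; one detected by Period 1 Day 15 would be labelled correctly.

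These shares assume the two SAP 5.1 sequences, dosing as assigned and the scheduled samples only. They count labels, not expected positives, and do not depend on how many participants completed before the study was terminated (SAP 1.1). The endpoint is exploratory and descriptive, the drug-naive samples are collected, and Listing 39 allows case-by-case reconstruction. No primary conclusion is affected.

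**What to change.** In SAP 7.4.1, say whether *treatment group* means current treatment or sequence. Define antibody baseline as the last sample before the participant's first GSK3858279 dose. Define a treatment-emergent positive as a new positive, or a rise in titre, after that dose; the size of rise that counts must be stated, since the documents give none.

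In Table 2.25, report treatment-emergent incidence by sequence and period, keep pre-dose and Day 15 separate, and show pre-existing positives on their own line. Use one counting unit in both places; participants suits an incidence.

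The cost is one definition and one revised table. Samples and titres are already planned, so no new data are needed.
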